16.4 Secondary endpoints

16.4.1 Confirmatory secondary endpoints

There are no confirmatory secondary endpoints.

16.4.2 Supportive secondary endpoints

16.4.2.1 Number of bleeding episodes during prophylaxis

Annualised bleeding rate will be summarised and a 95% two sided confidence interval will be provided based on a negative binomial regression model with number of bleeding episodes requiring treatment with N9-GP (also referred to as breakthrough bleeding episodes) as the outcome variable, and adjusting for exposure time. For comparison with previous trials, a sensitivity analysis based on a Poisson regression model allowing for over-dispersion will also be performed.

Since it must be expected that some patients will withdraw, it becomes essential to account for how such withdrawals may affect the analyses of the prophylaxis effect. The analyses above already account for possible different treatment durations by using treatment duration as an offset. This is a proper adjustment if withdrawal is not related to the observed bleeding frequency. However, since it is possible that patients will withdraw exactly because of the observed bleeding rate it is important to perform sensitivity analyses that may account for withdrawn patients possibly being qualitatively different from completing patients.

Specifically, this will be done by performing sensitivity analyses for all prophylaxis analyses using a last observation carried forward (LOCF) approach for all patients with at least 1 month prophylaxis treatment duration by calculating the yearly bleeding episode rate for withdrawn patients and use that as an endpoint. As an example; a patient with 6 bleeding episodes in 4 months will have an endpoint value of 18 corresponding to a maintained bleeding rate of 18 bleeding episodes per year. For patients withdrawing within 1 month this method is considered to give too uncertain LOCF values, hence imputation will not be attempted for such patients.

Annualised bleeding rate will also be summarised by type of bleeding episode.

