4.2.2 Secondary Endpoint

- Number and frequency of adverse events (AEs), serious AEs (SAEs) and Medical Events of Special Interest (MESI)*
- Number of breakthrough bleeding episodes during prophylaxis (annualised bleeding rate)*
- Haemostatic effect by 4-point haemostatic response scale (“excellent”, “good”, “moderate” and “poor”)*
- Incremental recovery at 30 minutes (IR30min), FIX activity at 30 minutes (C_{30min}) and trough level
- Amount of drug administered and number of doses needed to treat a bleeding episode

*Key supportive secondary endpoint prospectively selected for posting on (e.g. clinicaltrials.gov and EudraCT).

Protocol
 Trial ID: NN7999-3895
 UTN: U1111-1135-9557
 EudraCT No.: 2012-004867-38

~~CONFIDENTIAL~~

| | | |
|----------|------------------|---------------------|
| Date: | 05 November 2019 | Novo Nordisk |
| Version: | 8.0 | |
| Status: | Final | |
| Page: | 24 of 119 | |

5 Trial design

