8.6.1 Assessments of bleeding episodes and treatment response

The severity of bleeding episodes is defined as

- Mild/moderate: Bleeding episodes that are uncomplicated joint bleeding episodes, muscular bleeding episodes without compartment syndrome, mucosal- or subcutaneous bleeding episodes. These bleeding episodes can be treated at home after visit 20 and details of the bleeding episodes should be entered in the eDiary by the patient's parent(s)/LAR(s).
- Severe: All intracranial, retroperitoneal, iliopsoas and neck bleeding episodes must be categorised as severe. Muscle bleeding episodes with compartment syndrome and/or bleeding episodes associated with a significant decrease in the haemoglobin level (>3g/dl) should also be reported as severe (it is the investigators decision if haemoglobin measurements should be performed). The investigator must be contacted if a severe bleeding episode occurs.

In case of treatment requiring bleeding episode occurs outside the trial site's opening hours and prior to home treatment or treatment outside trial site (Section [5.3.5](#)) has been initiated, the patient must be treated according to local procedure.

Bleeding Episode - information to be collected

Information about bleeding episodes prior to the 20 ED (V20) should always be recorded in eCRF. In case the patient is treated outside the trial site the trial site should be informed in case of a bleeding episode and the details hereof. After 20 EDs bleeding episodes must be recorded either in the eDiary (if treated at home) or in the eCRF (if treated at the trial site), see Section [12.3](#).

Protocol
Trial ID: NN7999-3895
UTN: U1111-1135-9557
EudraCT No.: 2012-004867-38

~~CONFIDENTIAL~~

| | | |
|----------|------------------|---------------------|
| Date: | 05 November 2019 | Novo Nordisk |
| Version: | 8.0 | |
| Status: | Final | |
| Page: | 65 of 119 | |

Classification and recording of severe bleeding episodes is the responsibility of the investigator and should always be registered in the eCRF.

- Date and time the bleeding episode started
- Date and time the bleeding episode stopped
- Cause of the bleeding episode
 - i.e. spontaneous, traumatic or due to surgery
- Anatomical location of bleeding episodes
- Treatment of bleeding episodes
 - amount, date and time of each dose of N9-GP
- Severity of treatment requiring bleeding
 - mild/moderate, severe
- Haemostatic response assessed by the 4-point scale defined in the below [Table 8-3](#)

Protocol

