8.7.1 Minor surgery

Preventive N9-GP treatment before minor surgery including placement or removal of central venous access port can be performed within this trial at the investigator's discretion according to local guidelines. A dose of 40 IU/kg N9-GP prior to minor surgery is recommended to prevent perioperative bleeding episodes, see [Table 5-1](#). Definition of minor surgery, see Section [5.3.8](#). For minor surgery the following should be recorded in the eCRF:

- Date, time and volume of preventive dose before surgery
- Type of surgery
- Indication for surgery
- Location of surgery
- Date of surgery
- Start and stop date and time of surgery

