8.7.2 Major surgery

Major surgery can be performed while participating in the present trial. For definition of major surgery, see Section [5.3.8](#). Novo Nordisk must be contacted in due time prior to surgery, to ensure sufficient supply of N9-GP.

N9-GP dosing prior to, during and after surgery should aim at FIX activity levels as defined and recommended in the WFH Guidelines for the management of haemophilia.⁸ The preoperative N9-GP dose should aim at FIX activity level of approximately 100% which is expected to be achieved with dose of 40 or 80 IU/kg of N9-GP. Trough and peak levels, and incremental recovery of the particular patient must be taken into consideration by the Investigator when deciding the dose.

During the post-operative phase, clinical haemostatic response combined with close FIX activity monitoring is recommended to determine appropriate intervals for postoperative dosing of 40 IU/kg N9-GP. The dose interval should be adjusted in order to reach postoperative FIX activity levels as recommended by the WFH Guidelines for the management of haemophilia.⁸

It is the responsibility of the Investigator to determine when the patient must stop the weekly prophylaxis administrations of N9-GP prior to the surgery and when these should be resumed after the surgery. If the patient has not resumed weekly prophylaxis within 6 days from the day of surgery the reason must be documented. The first weekly prophylaxis dose after surgery should be omitted if it falls on the same day (\pm 1day) as the last postoperative dose. The following must be documented:

- Date and time the patient stops the weekly prophylaxis with 40 IU/kg N9-GP prior to the surgery
- Date and time the patient resumes the weekly prophylaxis with 40 IU/kg N9-GP after the post-surgery period

Protocol
 Trial ID: NN7999-3895
 UTN: U1111-1135-9557
 EudraCT No.: 2012-004867-38

~~CONFIDENTIAL~~

| | | |
|----------|------------------|---------------------|
| Date: | 05 November 2019 | Novo Nordisk |
| Version: | 8.0 | |
| Status: | Final | |
| Page: | 68 of 119 | |

During this period, all bleeding episodes and any haemostatic treatment administered must be recorded in the eCRF when the patient is at the site and in the eDiary when the patient is at home, refer to Section [12.3](#).

Perioperative procedures, assessments and blood sampling will be performed at the Investigators discretion and documented in the patients' medical records.

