Novo Nordisk A/S will be responsible for the statistical analysis.

The main statistical reporting of the trial will be performed when at least 20 patients have completed main phase (minimum 50 weeks) with at least 50 EDs and completed visit 23. Data from patients not yet having completed main phase and data from patients that have entered extension phase at this point will be included up to latest visit prior to this cut-off date. The data will be presented for the main phase and extension phase separately as well as combined. Except for the confidence interval for inhibitor rate and for annualised bleeding rate, the evaluation of data will be based on descriptive statistics, i.e. summary tables, listings and figures.

An updated statistical reporting of the trial with supportive data will be performed when at least 40 patients have had at least 100 EDs. Data from all patients will be included up to latest visit prior this cut-off date. The data will be presented for the main + extension phase and the extended prophylaxis period (beyond 100 EDs) separately as well as combined.

All data will be reported separately in a final report when the trial is completed.

[figure not shown]

Figure 16–1 Individual patient flow and time period for main trial report

Protocol
 Trial ID: NN7999-3895
 UTN: U1111-1135-9557
 EudraCT No.: 2012-004867-38

~~CONFIDENTIAL~~

| | | |
|----------|------------------|---------------------|
| Date: | 05 November 2019 | Novo Nordisk |
| Version: | 8.0 | |
| Status: | Final | |
| Page: | 97 of 119 | |

Multiple bleeding locations occurring from the same event (e.g. due to a fall) or at the same time point will be counted as one bleeding episode.

All bleeding endpoints will be evaluated based on bleeding episodes treated with N9-GP unless the bleeding was considered clinically insignificant (non-treatment requiring bleeding episode) and the associated treatment given was part of prophylaxis.

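### The prophylaxis bleeding rate counts treated bleeds caused by surgery as breakthrough bleeds, and no rule covers peri-operative time

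*Protocol*

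**What the plan says.** Protocol Section 4.2.2 lists the ABR during prophylaxis as a secondary endpoint and marks it as one of the key ones selected for public posting. Section 16.4.2.1 fits a negative binomial model with the "number of bleeding episodes requiring treatment with N9-GP (also referred to as breakthrough bleeding episodes) as the outcome variable" and gives a two-sided 95% interval.

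Section 16 sets the general counting rule: "All bleeding endpoints will be evaluated based on bleeding episodes treated with N9-GP unless the bleeding was considered clinically insignificant". The rest of that sentence adds that the treatment must also have been part of prophylaxis. This is the only exception.

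Section 8.6.1 requires the cause of each bleed, "i.e. spontaneous, traumatic or due to surgery".

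For follow-up time, Section 16.4.2.1 refers to exposure time and says that differing durations are handled "by using treatment duration as an offset". It does not mention surgery.

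For minor surgery, Section 8.7.1 lists "Date, time and volume of preventive dose before surgery" together with the type, indication, location, date and times of the procedure. For major surgery, Section 8.7.2 also requires "Date and time the patient stops the weekly prophylaxis with 40 IU/kg N9-GP prior to the surgery", and the matching restart.

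Section 16.4.2.1 further plans an ABR by type of bleeding episode, without saying what type means. The SAP covers only the neurocognitive data and has no rule for bleeding.

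**The concern.** The ABR is meant to show how well weekly prophylaxis prevents bleeding. A bleed from an incision is a complication of the procedure and says little about that. The plan collects the variable that separates the two but does not use it to define the endpoint.

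The gap matters most for minor procedures. Section 5.3.8 lists port implantation and removal, circumcision and simple dental work as examples, all of which can occur in boys under 6 at entry. It describes minor surgery as needing a single dose beforehand, so weekly dosing need not stop and a resulting bleed falls within prophylaxis.

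The main conclusion will be drawn from main-phase data once at least 20 patients have 50 exposure days (Section 16.6). The bleed count at that point may be small enough for one or two surgical bleeds to move the posted rate visibly.

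**Working it through.** **1. The plan's own figure.** Section 16.4.2.1 annualises 6 bleeds in 4 months as 18 per year: 6 / (4/12) = 18. This reproduces. If one of the six were surgical, the rate without it would be 5 / (4/12) = 15.

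**2. Does any rule remove a surgical bleed?**

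- *The exception in Section 16.* It needs a clinically insignificant bleed whose treatment was part of prophylaxis. A surgical bleed that itself required treatment does not meet it.
- *The restriction to prophylaxis.* After minor surgery, weekly dosing need not stop, so the bleed stays in. Around major surgery the documented stop and restart would allow removal, but no rule says so.
- *The summary by type.* Type is undefined. Even if it meant cause, a breakdown would not change the headline rate or its interval.
- *The SAP.* It adds nothing on the ABR.

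So a treated surgical bleed in a child on weekly prophylaxis counts.

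**3. Size in a main-phase analysis.** From the documents: 20 patients, 50 exposure days, weekly dosing. Assumed: every dose is a weekly prophylaxis dose, so 49 weeks separate the first dose from the fiftieth; ABR of 0.5, 1 or 2.

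Exposure = 20 × 49 / 52.18 = 18.8 patient-years. Expected non-surgical bleeds = ABR × 18.8. Effect of one surgical bleed = 1 / expected bleeds.

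| Assumed ABR | Expected bleeds | One surgical bleed |
|---|---|---|
| 0.5 | 9.4 | +10.6% |
| 1 | 18.8 | +5.3% |
| 2 | 37.6 | +2.7% |

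Time spent on pre-prophylaxis would shorten the exposure and raise these percentages. Additional patients at the cut-off would lower them.

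**4. Size with more exposure.** For 40 patients × 100 weeks: 40 × 100 / 52.18 = 76.7 patient-years. Expected bleeds are 38.3, 76.7 and 153.3, so one surgical bleed adds 2.6%, 1.3% or 0.7%.

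**5. Peri-operative time.** Suppose five operations of 14 days each were left in the offset. That is 70 days out of 18.8 × 365.25 = 6,867, or 1.0%. Retained time lowers the rate; surgical bleeds raise it.

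**6. Both together.** Compare (non-surgical + surgical bleeds) / all time with non-surgical bleeds / (all time − peri-operative time), for an ABR of 1, five operations, 0.1 treated bleeds per operation and 6 or 14 peri-operative days each. With 20 × 50 weeks (19.2 patient-years) the first rate is 1.6% to 2.2% higher. With 76.7 patient-years it is 0.4% to 0.5% higher.

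**The case against.** The strongest reply is that an all-cause rule is defensible. A bleed in a child still on weekly dosing did occur during prophylaxis. Some procedures will also fall in pre-prophylaxis, where Section 8.1.1.1 lists minor surgery, and those bleeds are outside this endpoint. One bleed is also small against the sampling error: for 9 observed bleeds the exact Poisson 95% interval is about 4.1 to 17.1, that is −54% to +90%, and over-dispersion would widen it. All of this stands, and it limits the severity. It does not settle which rate should be the headline when cause is recorded for each bleed.

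A reader might infer three stronger points that the documents do not support:

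- *That the plan keeps peri-operative time in the offset.* Section 16.4.2.1 says only exposure time and treatment duration, under a heading limited to prophylaxis. Section 8.7 treats the return to regular prophylaxis after surgery as a separate step, and the major-surgery dates permit exclusion. The defect is silence: two analysts could choose differently.
- *That the rate could be inflated by about a third.* That needs three surgical bleeds in 20 children and an ABR of 0.5 at the same time (3 / 9.4 = 32%). Nothing in the documents makes that combination likely.
- *That comparison with previous trials is damaged.* The documents do not say whether those trials counted surgical bleeds. If they did, the all-cause rate is the comparable one.

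**Conclusion.** The point holds for the numerator. As written, the headline ABR includes treated bleeds caused by surgery, and neither the restriction to prophylaxis nor the summary by type removes those that follow minor procedures. On the assumptions in step 3, each such bleed raises a main-phase ABR by about 11%, 5% or 3%, and by less in the combined or later analyses. How many will occur cannot be judged from the documents.

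For time at risk, the plan lacks a rule; the likely effect is about 1% or less for a handful of operations.

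Severity is low. Section 16.4.1 states that there are no confirmatory secondary endpoints, and no test or threshold depends on the ABR. The change is worth making because it costs little and brings a posted endpoint closer to the prophylaxis effect that it is meant to describe.

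**What to change.** Amend Section 16.4.2.1, or put the same text in an analysis plan that covers bleeding, before database lock:

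- Estimate the headline ABR without bleeds whose recorded cause is surgery, and report those bleeds on a separate line.
- Give the all-cause ABR and its interval alongside as a sensitivity analysis.
- Define type of bleeding episode so that it includes cause.
- Remove the documented stop-to-resume window around major surgery from both the bleed count and the offset.

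The cause field deals with minor surgery, so no new data are needed and treatment is unaffected. The cost is a few sentences and one extra model run. The all-cause rate must stay visible, in case earlier trials counted surgical bleeds.

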6.1 Number of patients

Number of patients planned to be screened: 60

Number of patients planned to be started on trial product: 60

Number of patients expected to complete the trial: 40

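### The LOCF withdrawal check overstates the bleeding rate if patients leave because of observed bleeding, and its gap from the main estimate cannot show which to believe

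*Protocol*

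**What the plan says.** Protocol Section 16.4.2.1 estimates the ABR "based on a negative binomial regression model with number of bleeding episodes requiring treatment with N9-GP", accounts for unequal follow-up "by using treatment duration as an offset", and states that "a 95% two sided confidence interval will be provided". For comparison with earlier trials, "a sensitivity analysis based on a Poisson regression model allowing for over-dispersion will also be performed".

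Of the offset it says: "This is a proper adjustment if withdrawal is not related to the observed bleeding frequency". It then names the threat: "since it is possible that patients will withdraw exactly because of the observed bleeding rate it is important to perform sensitivity analyses". The same sentence adds that those who withdraw may differ in kind from those who complete. The remedy is: "Specifically, this will be done by performing sensitivity analyses for all prophylaxis analyses using a last observation carried forward (LOCF) approach". It applies to patients with at least 1 month of prophylaxis, and the worked example turns 6 bleeds in 4 months into an endpoint of 18. Patients who leave within 1 month are not imputed. The section does not say what exposure or weight goes with the yearly value.

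The supplied SAP covers only the neurocognitive data (SAP Section 6) and adds nothing on ABR. Protocol Section 6.1 plans 60 patients started on product and gives "Number of patients expected to complete the trial: 40".

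**The concern.** A patient who leaves because his observed rate is high has, on average, a recorded rate above his true one. LOCF freezes that rate for the rest of the year, with no regression to the mean, and analyses the result as if it had been observed.

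Withdrawal that depends only on recorded bleeds is missing at random. A correctly specified negative binomial likelihood with an offset therefore remains valid under it. The protocol's condition that the offset is proper only when withdrawal is unrelated to observed bleeding is too restrictive for that likelihood. It describes the Poisson model better when patients differ in their rates.

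The main model fails where bleeding after withdrawal is worse than the recorded history predicts. LOCF has no adjustable assumption for that. ABR is a key supportive secondary endpoint chosen for public posting (Protocol Section 4.2.2). In a single-arm trial the estimate and its interval are the result, so a misread robustness check matters.

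**Working it through.** **The plan's own figure.** Yearly value = bleeds ÷ years observed. 6 ÷ (4/12) = 18, which reproduces the protocol's example. At the 1-month limit, one bleed gives 1 ÷ (1/12) = 12.

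**What a gamma-Poisson model would predict.** With mean rate μ, dispersion d, k = 1/d, y bleeds and t years, the patient's expected rate is (k + y) ÷ (k/μ + t). The values of μ and d are assumptions.
- μ = 1.5, d = 0.5 (k = 2), 6 bleeds in 4 months: (2 + 6) ÷ (1.333 + 0.333) = 4.8 per year, against 18 carried forward.
- μ = 3, d = 1 (k = 1), same history: (1 + 6) ÷ (0.333 + 0.333) = 10.5 per year.
- μ = 1.5, d = 0.5, 1 bleed in 1 month: (2 + 1) ÷ (1.333 + 0.083) = 2.1 per year, against 12.

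**Simulation.** Bleeds follow a Poisson process with a patient-specific rate.
- *Setting A:* 40 patients, 1 year, true ABR 1, 1.5 or 3, dispersion 0.5 or 1. Review is monthly from month 1, with withdrawal probability p per month while the observed rate exceeds twice the mean.
- *Setting B:* 50 patients, 1 or 2 years, with withdrawal possible once the observed rate passes 4 or 6 per year. Rows marked B in the table below use true ABR 2, except the underlying-rate row, which covers a wider grid.

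Bias against the true ABR:

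| Withdrawal follows | Setting | Negative binomial offset | LOCF |
|---|---|---|---|
| Observed rate | A, p = 0.03 (4–6% withdrawn) | within about 2% | +5% to +11% |
| Observed rate | A, p = 0.1, two runs | within about 2% | +12% to +31% |
| Observed rate | A, p = 0.3, two runs | within about 4% | +31% to +72% |
| Observed rate | B, log-normal patient rates | −1% to −5% | +17% to +53% |
| Observed rate | B, two-point patient rates | +5% to +19% | +24% to +66% |
| Observed rate | B, zero-inflated patient rates | +4% to +26% | +20% to +63% |
| Underlying rate | A, two runs | 4–20% low | within about 3% |
| Underlying rate | B | −2% to −20% | +2% to −11% |

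Milder triggers shrink the LOCF bias. In setting A with dispersion 0.5, requiring at least 3 bleeds before withdrawal gave +3% to +17%. Starting review at month 6 gave +2% to +13%. Purely random withdrawal left both methods within about 2.5%.

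**Intervals.** In one setting A run with observed-rate withdrawal, 95% interval coverage was 91–94% for the offset model. For LOCF it was 77–90% at p = 0.1 and 46–75% at p = 0.3.

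**Can the gap discriminate?** Take true ABR 1, dispersion 1, p = 0.3.
- Observed-rate withdrawal: main model 1.02, LOCF 1.63. The main model is right.
- Underlying-rate withdrawal: main model 0.81, LOCF 1.00. LOCF is right.

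The gap has the same sign both times (1.63 ÷ 1.02 = 1.60; 1.00 ÷ 0.81 = 1.23).

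**The Poisson model.** Its point estimate is total bleeds over total time. Under observed-rate withdrawal it was 4–18% low in setting A and up to 47% low elsewhere when patients differed in their rates.

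**The case against.** **The sizes come from assumed triggers.** This stands. At ABR 1 the setting A rule is severe: one bleed in month 1 exceeds the threshold at reviews 1 to 5, so at p = 0.3 the chance of leaving is 1 − 0.7⁵ = 83%. Any percentage is conditional.

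**LOCF serves the protocol's second rationale.** This also stands. If withdrawn patients differ in their underlying rate, LOCF is usually the better estimate. A reader might infer that LOCF is simply wrong and the main model right; the section's wording covers both scenarios and does not support that.

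**The main model's near-unbiasedness rests on its gamma assumption.** True: the bias reached +26% with zero-inflated rates, although LOCF was still worse there.

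**A third of patients would be imputed.** A reader might infer this from 60 started and 40 completing (20 ÷ 60). The documents do not support it. Protocol Section 16.1 takes 40 completers from the EMA guideline, and no causes of non-completion are forecast. No mandatory withdrawal criterion in Section 6.4 is a high bleeding rate. Bleeding-related exit remains possible, because lack of efficacy is a listed reason (Section 8.1) and a poor haemostatic response prompts the investigator to reconsider participation.

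**Impact is small.** Largely accepted. Section 16.4.1 has no confirmatory secondary endpoints, ABR is not tested, and an upward bias is conservative for efficacy. Agreement between the two estimates would also be reassuring. What remains is that a disagreement could not be interpreted.

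**Conclusion.** The concern holds in conditional form. If withdrawal follows the observed bleeding rate, LOCF overstates the ABR by a few percent to over 60%, depending on ABR, dispersion and withdrawal rule. The negative binomial offset model is then much less biased, if gamma-distributed patient rates are a fair description. If withdrawal follows the underlying rate, the main model is about 4–20% low in most settings and LOCF is usually closer. Because LOCF exceeds the main estimate either way, and treats imputed values as data, it cannot settle the question that the section raises.

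A reader might infer that this trial's reported ABR will be wrong by some stated percentage. The documents do not support that: they give no expected ABR, dispersion or bleeding-related withdrawal rate, and LOCF is a sensitivity analysis beside the main estimate. The primary endpoint, inhibitor incidence, is unaffected.

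**What to change.** In Section 16.4.2.1, make the withdrawal sensitivity analysis a multiple imputation of withdrawn patients' unobserved prophylaxis time.
- State a fixed horizon for each report, for example the end of the main phase for the main report.
- Draw each patient's rate from the fitted gamma-Poisson model, given his own bleeds and exposure.
- Multiply that rate by pre-set factors of 1, 1.5, 2 and 3, and draw the missing bleeds.
- Combine with Rubin's rules and report the ABR and 95% CI at each factor.
- Include patients who withdraw within 1 month; the model shrinks short histories.
- Keep LOCF as an additional row for comparison with earlier trials, labelled as biased upward if withdrawal follows observed bleeding.

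In simulation with true ABR 1.5, factor 1 gave 1.51 under observed-rate withdrawal. Under underlying-rate withdrawal, factors 1 to 2 ran from 1.39 to 1.52. Where the main model is further off, the larger factor is needed; factors 1 to 3 bracketed the truth in a further run.

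The cost is protocol or SAP wording and a short program, with no new data or patients. The factors and horizon must be fixed in advance. The imputation relies on the gamma rate model, and factors of 1 or more cannot correct an upward bias that arises when that model fits badly.

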6.4 Withdrawal criteria

The patient may withdraw at will at any time either by the patient or by the patient's parent(s) or the patient's LAR. The patient's request to discontinue must always be respected.

The patient may be withdrawn from the trial at the discretion of the investigator due to a safety concern or if judged non-compliant with trial procedures.

The patient must be withdrawn if the following applies:

1. Dosed in the trial, but not fulfilling the inclusion and/or exclusion criteria
2. Development of FIX inhibitors ≥ 5 BU confirmed by two consecutive tests (central laboratory) and associated with N9-GP binding antibodies (the patient must be withdrawn from N9-GP treatment upon confirmation of FIX inhibitor ≥ 5 BU and attend three inhibitor follow-up visits)
3. Anaphylactic reaction to the trial product, for definition see section [11.1](#)
4. Major surgery prior to 20 EDs. see section [5.3.8](#)
5. Significant thromboembolic event, see Section [11.1](#)
6. Incapacity or unwillingness to follow trial procedures
7. Participation in another clinical trial while participating in this trial

If a patient experiences treatment failure where haemostatic response is rated as poor according to Section [8.6](#), the investigator should consider if it is in the patient's best interest to continue in the trial.

All data collected prior to withdrawal will be used in the trial analyses.

Temporary or permanent discontinuation of treatment with trial product will not lead to withdrawal from the trial.

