6.6.3 Rationale for withdrawal criteria

- Criteria nos. 1-7 are included to protect the patient's safety and reliability of the data.

Protocol
 Trial ID: NN7999-3895
 UTN: U1111-1135-9557
 EudraCT No.: 2012-004867-38

~~CONFIDENTIAL~~

| | | |
|----------|------------------|---------------------|
| Date: | 05 November 2019 | Novo Nordisk |
| Version: | 8.0 | |
| Status: | Final | |
| Page: | 34 of 119 | |

7 Milestones

Planned duration of recruitment period: First patient first visit (FPFV) to last patient first visit (LPFV): 75 months

First Patient First Visit: 02-Jul-2014

Planned Last Patient First Visit: 30-Sep-2020

End of trial is defined as Last Patient Last Visit: 30-Oct-2022

The duration of N9-GP treatment in the trial is a minimum of 100 EDs for at least 40 patients and will continue until Last Patient Last Visit for the trial, which will be 30 October 2022.

Planned completion of clinical trial report (CTR): Q2 2023

Recruitment

The screening rate will be followed closely via the interactive web response system (IWRS) in order to estimate when to stop screening. All investigators will be notified immediately when the recruitment period ends, after which no further consent will be sought from additional families and the IWRS will be closed for further screening, unless additional screening is needed due to patient replacement.

All subjects included in the screening period and eligible for the trial will enter the trial.

Trial registration

Information of the trial will be disclosed at clinicaltrials.gov, novonordisk-trials.com and clinicaltrials.jp. According to the Novo Nordisk Code of Conduct for Clinical Trial Disclosure, it will also be disclosed according to other requirements such as those of the International Committee of Medical Journal Editors (ICMJE)¹¹, the Food and Drug Administration Amendment Act (FDAAA)¹², European Commission Requirements¹³ and other relevant recommendations or regulations. If a patient requests to be included in the trial via the Novo Nordisk e-mail contact at these web sites, Novo Nordisk may disclose the investigator's contact details to the patient. As a result of increasing requirements for transparency, some countries require public disclosure of investigator names and their affiliations.

Protocol
 Trial ID: NN7999-3895
 UTN: U1111-1135-9557
 EudraCT No.: 2012-004867-38

~~CONFIDENTIAL~~

Date: 05 November 2019
 Version: 8.0
 Status: Final
 Page: 35 of 119
Novo Nordisk

8 Methods and assessments

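### Does the LOCF check on bleeding rate fail because no exposure is stated for the yearly value given to withdrawn patients?

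*Protocol*

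**What the plan says.** Section 16.4.2.1 models the number of treated bleeds by negative binomial regression, with an over-dispersed Poisson model for comparison with earlier trials. On exposure it says: "The analyses above already account for possible different treatment durations by using treatment duration as an offset". Because patients may leave on account of their bleeding, it adds a check described as "performing sensitivity analyses for all prophylaxis analyses using a last observation carried forward (LOCF) approach". The check covers patients with at least one month of prophylaxis and works by "calculating the yearly bleeding episode rate for withdrawn patients and use that as an endpoint". In the worked example, 6 bleeds in 4 months give a value of 18, "corresponding to a maintained bleeding rate of 18 bleeding episodes per year". No exposure is attached to that value, and nothing is said about how completers enter the same analysis.

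The SAP does not fill the gap, because its scope (section 6) is the neurocognitive data only. Section 16 of the protocol plans a main report at 50 exposure days (EDs), an updated report at 100 EDs and a final report. For the updated report: "The data will be presented for the main + extension phase and the extended prophylaxis period (beyond 100 EDs) separately as well as combined". Section 6.4 adds: "All data collected prior to withdrawal will be used in the trial analyses".

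**The concern.** In a count model the offset sets how much each patient weighs. The natural reading of a yearly value is one year of exposure. In the main phase that causes no trouble, because prophylaxis there lasts roughly 30 to 50 weeks (50 EDs, less up to 20 spent on pre-prophylaxis).

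The later reports cover several years. Section 7 gives "First Patient First Visit: 02-Jul-2014" and "Planned Last Patient First Visit: 30-Sep-2020", with the trial ending on 30 October 2022. If a withdrawn patient observed for three years were given one year while completers kept their full time, he would count for less than in the main analysis. Should such patients be the heavy bleeders, the check would lower the rate and could be read as reassurance, the opposite of its purpose. It would also appear to set aside observed time, against section 6.4.

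**Working it through.** **The plan's own figure.** 6 × 12/4 = 18 per year, as stated. Paired with one year, the rate stays 18. Paired with the observed four months, it becomes 18/(4/12) = 54 per year, which contradicts the maintained rate of 18 in the example. That reading is excluded. What stays open is how completers enter.

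**Reporting span.** 2 July 2014 to 30 October 2022 is 8.33 years; 30 September 2020 to 30 October 2022 is 2.08 years. Both are upper limits for prophylaxis time, because the open screening interval (section 8.1.1) and pre-prophylaxis (section 5.3.2) come first.

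**Weights.** In an intercept-only Poisson model a patient's weight is proportional to his time t. One year in place of t multiplies it by 1/t: 3.0 for exit at 4 months, 0.50 at 2 years, 0.33 at 3 years. In the negative binomial model the weight is proportional to t/(1 + kμt). With μ = 1 per year and exit at 3 years, the ratio is 0.56, 0.67 and 0.78 for k = 0.5, 1 and 2, so the loss is smaller.

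**Assumed case.** The documents give no bleeding rates or leaving times. Assume 30 completers at 0.5 bleeds per year, 10 withdrawn patients at 4 per year, and dispersion 0.8. Poisson rate = total bleeds/total time, in a four-year report:

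- Main analysis, all exits at 3 years: (60 + 120)/(120 + 30) = 1.20. Exits at 4 months: (60 + 13.3)/(120 + 3.3) = 0.59.
- Mixed reading (one year for withdrawn, four for completers): (60 + 40)/(120 + 10) = 0.77.
- Carried to four years: (60 + 160)/160 = 1.375.
- One yearly value for every patient: (30 × 0.5 + 10 × 4)/40 = 1.375.

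The last two agree for a simple reason: with equal exposures, the fitted rate in either model is total bleeds over total time.

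Negative binomial, mean of 400 simulated trials per case, four-year report:

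| Exit of withdrawn patients | Main analysis | Mixed reading | Carried to four years |
|---|---|---|---|
| All at 4 months | 0.91 | 1.23 (+36%) | 1.37 |
| All at 1 year | 1.21 | 1.21 (0%) | 1.36 |
| Half at 4 months, half at 3 years | 1.17 | 1.22 (+4%) | 1.36 |
| All at 2 years | 1.32 | 1.21 (−8%) | 1.37 |
| All at 3 years | 1.35 | 1.20 (−11%) | 1.37 |

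**Main phase**, exit at 4 months: 1.18 / 1.40 / 1.37, so the rule works as intended there.

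**Final report on the trial calendar**, exits spread evenly from one month to end of trial: 1.25 / 1.17 / 1.35 (−6%); a separate run gave 1.28 / 1.19 / 1.37 (−7%), with one yearly value for everyone also at 1.37. A shorter prophylaxis span of 1 to 6.8 years gives 1.29 / 1.26 (−2%). If all leave in the first year, the shift is +21%. With the Poisson model, even spread, the rates are 0.99 / 0.70 / 1.35 (−29% for the mixed reading). If withdrawn patients bleed like completers, all three methods give 0.50.

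**Against precision.** The log-rate standard error is about 0.23. The largest fall in the table, ln(1.204/1.351) = −0.115, is half of that; the even-spread fall, ln(1.173/1.251) = −0.064, is under a third.

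**The case for a change.** The case for acting is that the rule applies the yearly rate to withdrawn patients only, so the mixed reading is the more literal one. It sets a lower limit of one month and no upper limit, so late leavers are included. Under even withdrawal on the trial calendar, the mixed reading fell below the main analysis in 85% of simulated trials, and the Poisson fall is large. The annualised bleeding rate is also a key supportive endpoint chosen for registry posting (section 4.2.2), and an offset is best fixed before results are seen.

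The omission stands, and so does the arithmetic for the mixed reading. The step to harm is weaker. The direction rests on withdrawn patients bleeding eight times as often as completers and on 79% of them leaving after year one; no passage supports either. The Poisson model is itself a secondary comparison.

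Section 6.4 is not breached. Each yearly value is computed from all of a patient's observed bleeds and time, and the main model uses the full record.

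Writing a longer carry-forward into the plan would not clearly be better. If all leave in year one, it stretches about 21 observed bleeds in 5.5 patient-years into about 206 in 52. Counting one week per missing ED would overlook that bleed and surgery doses also count as EDs (sections 5.3 and 5.3.8). Separate horizons would also be needed for the extension phase and for the period beyond 100 EDs.

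**Conclusion.** The gap is real but small, and of the kind analysts close when they write the program. The model cannot be fitted without an exposure for every patient, and the sensible choice is to put all patients on one basis, which gives the intended upward movement (about 1.37 in the assumed case). Only the mixed reading, together with late exit of heavy bleeders, turns the check downward: about 2% to 7% in the negative binomial model with even withdrawal on the trial calendar, 11% in the most adverse case shown, and about 29% in the Poisson comparison. Early exits and the main phase behave as planned.

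These sizes rest on assumed rates, dispersion and leaving times. The check serves a supportive endpoint: section 16.4.1 names no confirmatory secondary endpoint, and section 16.6 draws the main conclusion from main-phase data and calls the later reports supportive. The primary inhibitor analysis does not use it. No change to the plan is needed.
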